### **11.3 Recording Adverse Events**

The following subsections detail what information must be documented for each adverse event occurring during the time period specified in Section 11.4.

At each contact with the subject, the investigator must seek information on adverse events by specific questioning and, as appropriate, by examination. Information on all adverse events should be recorded immediately in the source document, and also in the appropriate adverse event module of the case report form (CRF). All clearly related signs, symptoms, and abnormal diagnostic procedures results should be recorded in the source document, though should be grouped under one diagnosis.

All adverse events occurring during the study period must be recorded.

The clinical course of each event should be followed until resolution, stabilization, or until it has been determined that the study treatment or participation is not the cause. Serious adverse events that are still ongoing at the end of the study period must be followed up to determine the final outcome. Any serious adverse event that occurs after the study period and is considered to be possibly related to the study treatment or study participation should be recorded and reported immediately.

### **11.3.1 Relationship to Study Intervention**

The relationship to study intervention or study participation must be assessed and documented for all adverse events. Evaluation of relatedness must consider etiologies such as natural history of the underlying disease, concurrent illness, concomitant therapy, study-related procedures, accidents, and other external factors.

The following guidelines are used to assess relationship of an event to study intervention:

1. Related (Possible, Probable, Definite)
  - a. The event is known to occur with the study intervention.
  - b. There is a temporal relationship between the intervention and event onset.
  - c. The event abates when the intervention is discontinued.
  - d. The event reappears upon a re-challenge with the intervention.
2. Not Related (Unlikely, Not Related)
  - a. There is no temporal relationship between the intervention and event onset.
  - b. An alternate etiology has been established.

### **11.3.2 Expectedness**

The PI is responsible for determining whether an AE is expected or unexpected. An AE will be considered unexpected if the nature, severity, or frequency of the event is not consistent with the risk information previously described for the intervention. Risk information to assess expectedness can be obtained from preclinical studies, the investigator's brochure, published medical literature, the protocol, or the informed consent document.

### **11.3.3 Severity of Event**

Adverse events will be graded for severity according to the Common Terminology Criteria for Adverse Events (CTCAE) version 4.0.

### **11.3.4 Intervention**

Any intervention implemented to treat the adverse event must be documented for all adverse events.

## 11.4 Safety Reporting

The study period during which adverse events must be reported is normally defined as the period from the initiation of any study procedures to the end of the study treatment follow-up. For this study, the study treatment follow-up is defined as 30 days following the last administration of study treatment.

For patients whose Oncotype Dx recurrence score is unknown and who sign the molecular pre-screening ICF, AEs which occur after signature of this consent will only be captured if they meet the definition of serious as outlined in Section 11.1.2 and are reported to be causally related with study procedures (e.g. an invasive procedure such as biopsy). Once the main study ICF is signed, all AEs per the descriptions below will be captured in the Adverse Event CRF.

Patients whose Oncotype Dx recurrence score is known will sign the main study ICF.

For patients with unknown Oncotype Dx Recurrence Scores and who sign the molecular pre-screening ICF, SAE collection will start upon signing the molecular pre-screening ICF. SAEs will only be reported if the event is suspected to be causally related to a study procedure as assessed by the investigator (e.g. an invasive procedure such as biopsy). SAEs will be followed until resolution or until clinically relevant improvement or stabilization. If the main ICF is not signed (molecular screen failure), SAE collection ends 30 days after the last study related procedure.

For patients with known Oncotype Dx Recurrence Scores who sign the main study ICF, SAE collection starts at time of main study informed consent whether the patient is a screen failure or not.

### 11.4.1 Reporting to IRB

#### 11.4.1.1 Unanticipated Problems

All incidents or events that meet criteria for unanticipated problems (UAPs) as defined in Section 11.1.1 require the creation and completion of an unanticipated problem report form (OHR-20).

UAPs that pose risk to participants or others, and that are not AEs, will be submitted to the TJU IRB on an OHR-20 form via the eazUP system within 10 working days of the investigator becoming aware of the event.

UAPs that do not pose risk to participants or others will be submitted to the TJU IRB at the next continuing review.

Participating sites will submit UAPs to their local IRB per local institutional requirements. Participating sites will provide TJU with a copy of all UAP reports.

#### **11.4.1.2 Adverse Events**

Grade 1 AEs will be reported to the IRB at continuing review.

Grade 2 AEs will be reported to the IRB at the time of continuing review.

#### **11.4.1.3 Serious Adverse Events**

SAEs will be reported to the IRB on OHR-10 forms via the electronic reporting system (eSAEy) according to the required time frames described below.

Grade 3-4 AEs that are unexpected and deemed to be at least possibly related to the study will be reported to the IRB within 2 working days of knowledge of the event.

Grade 3-4 AEs that are deemed unrelated to the study will be reported to the IRB within 5 working days.

Grade 5 AEs will be reported to the IRB within one working day of knowledge of the event.

All SAEs will be submitted to the IRB at continuing review, including those that were reported previously.

#### **11.4.2 Reporting to SKCC DSMC**

On a quarterly basis, all AEs and SAEs, safety and toxicity data, and any corrective actions will be submitted to the DSMC per the DSMP. The quarterly report to DSMC will also include any unanticipated problems that in the opinion of the PI should be reported to the DSMC.

For expedited reporting requirements, see Appendix C: DSMC AE/SAE Reporting Requirements.

#### **11.4.3 Reporting to Drug Supplier**

The principal investigator has the obligation to report all serious adverse events to the IRB and the Novartis Pharmaceuticals Drug Safety and Epidemiology Department (DS&E).

To ensure patient safety, every SAE, regardless of suspected causality, occurring after the patient has provided informed consent and until at least 30 days after the patient has stopped study treatment/participation, must be reported to Novartis within 24 hours of learning of its occurrence. Information about all SAEs is collected and recorded on a Serious Adverse Event Report Form. The investigator must assess and record the relationship of each SAE to each specific study treatment (if there is more than one study treatment), complete the SAE Report Form in English, and **send the completed, signed form along with the Novartis provided fax cover sheet to the Novartis Oncology Drug Safety and Epidemiology (DS&E) department by fax ([contact]) within 24 hours.**

Any additional information for the SAE including complications, progression of the initial SAE, and recurrent episodes must be reported as follow-up to the original episode within 24 hours of the investigator receiving the follow-up information. An SAE occurring at

---

a different time interval or otherwise considered completely unrelated to a previously reported one should be reported separately as a new event.

Any SAEs experienced after this 30 days period should only be reported to Novartis if the investigator suspects a causal relationship to the study drug. Follow-up information is submitted in the same way as the original SAE Report. Each re-occurrence, complication, or progression of the original event should be reported as a follow-up to that event regardless of when it occurs. The follow-up information should describe whether the event has resolved or continues, if and how it was treated, whether the blind was broken or not, and whether the patient continued or withdrew from study participation.

If the SAE is not previously documented in the Everolimus Investigator Brochure or Package Insert (new occurrence) and is thought to be related to the Novartis study drug, a DS&E associate may urgently require further information from the investigator for Health Authority reporting. Novartis may need to issue an Investigator Notification (IN), to inform all investigators involved in any study with the same drug that this SAE has been reported. Suspected Unexpected Serious Adverse Reactions (SUSARs) will be collected and reported to the competent authorities and relevant ethics committees in accordance with Directive 2001/20/EC or as per national regulatory requirements in participating countries.

## 11.1 Reporting for Subsites

All SAEs occurring at a participating site must be reported to the Thomas Jefferson University clinical study coordinator and Novartis (per section 11.4.3) within 24 hours of notification. The initial notification can take place via email, followed by the submission of a formal report.

SAEs should be reported to Thomas Jefferson University's The Off-site OHR-10 form (or On-site OHR-10 for Network site or sites using the TJU IRB) located in Appendix D, and should comprise a full written summary, detailing relevant aspects of the adverse events in question, including grading and attribution to study drug. Where applicable, information from relevant hospital case records and autopsy reports should be included.

**SAE reports should be signed by the sub-site PI, and then faxed to the Thomas Jefferson University coordinator within 24 hours at: [contact] attention: [name].**

The TJU coordinator will notify the TJU PI and obtain the TJU PI signature, and report these events to the TJU Medical Monitor/IRB appropriately (within 5 working days if it deems an amendment, or in a spreadsheet at the time of annual review if no amendment is necessary).

Any non-reportable AE must be kept by the sub-site on an ongoing tracking log to be reviewed by TJU quarterly (see Appendix E).

Unanticipated problems (UAPs) occurring at participating sites that pose risk to subjects or others, and that are not AEs/SAEs, should be reported to TJU within 10 working days using

---

form OHR-20 and should be faxed to the Thomas Jefferson University coordinator within 5 days at: **[contact] attention: [name]**.

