## **11.2 Coordinating Site**

All reportable AEs/SAEs occurring at the coordinating site must be reported to TJU IRB/Medical Monitor using the On-site OHR-10 Form, and should comprise a full written summary detailing relevant aspects of the adverse events in question, including grading and attribution to study drug. Where applicable, information from relevant hospital case records and autopsy reports should be included.

Reportable AE/SAEs from TJU will then also be faxed to the Participating Site coordinator per same guidelines as outlined above.

All unexpected AE./SAEs that are probably or definitively related to the study procedures from either the participating site or the coordinating site must be reported to the TJU IRB within 48 hours of the TJU Principal Investigator being notified of the event.

Any on-study death (regardless of relationship) and any unforeseen death, that indicates that the participant or others may be at increased risk of harm, must be submitted to the TJU IRB/Medical Monitor within 24 hours of notification. Any unrelated SAE should be reported within 5 working days. The TJU study team will notify the TJU IRB appropriately.

Additional follow-up SAE reports should be submitted when available.

Unanticipated problems that pose risk to subjects or others, and that are not AEs/SAEs should be reported to TJU IRB within 10 working days using form OHR-20 and should be faxed to the Participating Site coordinator within 24 hours.

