## THOMAS JEFFERSON UNIVERSITY ADVERSE REACTION REPORT FORM

TO BE COMPLETED BY PRINCIPAL INVESTIGATOR WHEN AN ADVERSE REACTION (AE) OCCURS IN STUDIES CONDUCTED OFF-SITE.  
This Form Must Be Typewritten

**POLICY:** Any serious and/or unexpected (not in consent form) off-site adverse event (AE) that is deemed by the principal investigator to be probably or definitely related to the study drug, and that necessitates a change to the protocol and/or consent form, must be reported within five days of receipt of report. AEs judged to be unrelated to the drug, the result of progressive disease, or other factors such as accidents or unrelated medical procedures, need not be reported. (Consult IRB Policy & Procedures Handbook or website for more information.)

Principal Investigator/Department: \_\_\_\_\_ IRB Control #: \_\_\_\_\_  
Title of Project: \_\_\_\_\_

Sponsor (if applicable): \_\_\_\_\_ Study Drug(s)/Device: \_\_\_\_\_

Provide a brief and concise description of adverse reaction (no narrative, please):

Is this:	A new report? Yes  No 	Have you previously reported this adverse reaction to the IRB?
A follow-up report?	Yes  No 	For this study? Yes  No 
		For this patient? Yes  No 
		Date Reported: _____

How many times has this reaction occurred in individual patients participating in this study? \_\_\_\_\_ (usually in the company narrative)

What is the total national/international enrollment for the study? \_\_\_\_\_

In the Principal Investigator's opinion, was the event drug-related or caused by the procedures associated with this protocol?

(Circle One): UNRELATED PROBABLY RELATED DEFINITELY RELATED

If UNRELATED, DO NOT SUBMIT TO IRB. Keep report for your records.

Is the risk of this adverse reaction described in the consent form? Yes  No 

If Yes, DO NOT SUBMIT TO IRB. Keep report for your records.

If No, should this risk be described in the consent form? Yes  No 

If Yes, submit revision to consent form. (Provide 35 collated, stapled copies of OHR-12, revised consent form with changes highlighted, current stamped consent form, and adverse event report(s).)	If No, provide justification for not including this reaction as a risk in the consent form:
---	---

Has this AE changed the risk to benefit ratio of the study in any way? Yes  No  Explain: \_\_\_\_\_

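### For serious events at the participating site, Sections 11.4.1.3, 11.1 (subsites) and 11.2 (coordinating site) set conflicting rules for the coordinating centre's onward report to the IRB

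*Combined protocol and SAP*

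**What the plan says.** Five places in the protocol bear on when the IRB hears of an SAE at the participating site.

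- **Section 11.4.1.3 (Serious Adverse Events).** Unexpected grade 3-4 events that are "at least possibly related to the study will be reported to the IRB within 2 working days of knowledge of the event". Also: "Grade 3-4 AEs that are deemed unrelated to the study will be reported to the IRB within 5 working days". Grade 5 events go within one working day. All SAEs, including those already reported, go again at continuing review. Nothing limits this section to one site.
- **Section 11.1 (Reporting for Subsites).** Every participating-site SAE goes to the coordinating centre's study coordinator and the drug supplier within 24 hours. The coordinator obtains the lead investigator's signature and then reports to the medical monitor and IRB "within 5 working days if it deems an amendment, or in a spreadsheet at the time of annual review if no amendment is necessary".
- **Section 11.2 (Coordinating Site).** "All unexpected AE./SAEs that are probably or definitively related to the study procedures", at either site, go to the IRB within 48 hours of the lead investigator being notified. Unrelated SAEs have 5 working days, and on-study deaths 24 hours.
- **Section 11.3.1.** Possible, probable and definite all count as related.
- **Appendix D, off-site OHR-10 form.** Section 11.1 assigns this form to subsites, with the on-site version for sites that use the coordinating centre's IRB. The off-site form requires a report within five days only if the event is probably or definitely related and forces a change to the protocol or consent form. Its causality line offers unrelated, probably related and definitely related. It adds: "If UNRELATED, DO NOT SUBMIT TO IRB. Keep report for your records", and says the same of risks already in the consent form.

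For unanticipated problems, one sentence of Section 11.1 (subsites) gives 10 working days to report to the coordinating centre, and then says that the form "should be faxed to the Thomas Jefferson University coordinator within 5 days".

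**The concern.** The three sections use different triggers. Section 11.4.1.3 turns on grade, expectedness and causality, with possible relation enough. Section 11.2 turns on expectedness and causality, with possible relation not enough. Section 11.1 (subsites) turns only on whether the protocol has to be amended. No statement gives one section precedence, and the coordinator handling a second-site event would naturally follow the section headed for subsites.

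At stake is timely IRB oversight of unexpected, related serious events, the class that Section 11.4.1.3 singles out for its 2-day deadline. Under the subsite rule, such an event can wait for the annual spreadsheet when no amendment is judged necessary. The same event at the coordinating centre would reach the IRB within days.

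**Working it through.** No arithmetic figure is stated in the plan on this point, so the check is to set the rules side by side. The case is a grade 3-4 SAE at the participating site.

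| Event | 11.4.1.3 | 11.1 Subsites, amendment needed | 11.1 Subsites, no amendment | 11.2 Coordinating Site |
|---|---|---|---|---|
| Unexpected, possibly related | 2 working days | 5 working days | annual review | no deadline |
| Unexpected, probably or definitely related | 2 working days | 5 working days | annual review | 48 hours |
| Expected, related | continuing review only | 5 working days | annual review | no deadline |
| Unrelated | 5 working days | 5 working days | annual review | 5 working days |

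The sentence in 11.2 on unrelated SAEs does not name the sites. The conflict in the last row stands on 11.4.1.3 alone.

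**Count of cases.** Four causality levels (unrelated, possible, probable, definite) x expected or unexpected x amendment or not gives 4 x 2 x 2 = 16.

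- Unexpected and related: 3 x 2 = 6 cases. In all six, 11.1 allows a later report than 11.4.1.3.
- Unrelated, no amendment: 2 cases. 11.1 allows annual review where 11.4.1.3 sets 5 working days.
- Unrelated, amendment needed: 2 cases. The three sections agree on 5 working days.
- Expected and related: 3 x 2 = 6 cases. 11.4.1.3 sets no expedited deadline. 11.1 sets one only in the 3 cases that need an amendment.

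So in 6 + 2 = 8 of the 16 cases the subsite rule permits a later IRB report than 11.4.1.3 requires. These are combinations of circumstances, not frequencies of events. Where annual review applies, the wait can be up to about 12 months, depending on when in the review year the event falls.

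**Can the sections be reconciled as they stand?** One could read 11.4.1.3 as covering the coordinating centre and 11.1 with Appendix D as covering the second site. Two passages defeat that reading. Section 11.2 expressly brings participating-site events under its 48-hour rule, and Section 11.4.3 obliges the principal investigator to report all SAEs to the IRB.

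**The off-site form.** If the second site uses it, a possibly related event cannot be marked as such and does not meet the form's own trigger for a report. Unrelated and consent-listed events are expressly kept back. With the form as a fourth source, all four coincide in none of the 16 cases. The documents do not say which IRB, and so which form, the second site uses for SAEs. Section 11.4.1.1 mentions the local IRB only for unanticipated problems. If the on-site form applies, this limb falls away and the table above is unchanged.

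**The case against.** The best case for the plan is that little is lost in practice. Every subsite SAE reaches the coordinator and the drug supplier within 24 hours, with no causality filter, and the lead investigator must sign it. Deaths have one working day in 11.4.1.3 and 24 hours in 11.2. Appendix C, though its table is broken in the text, shows expedited entries of 48 hours and 5 working days for the monitoring committee and a row that includes possible relation. The subsite's written summary must state attribution, so possible relation can be recorded despite the form. For probable or definite relation, 2 working days and 48 hours are close. A coordinator who always took the shortest deadline would meet all three sections. All of this stands, and it confines the problem to the coordinating centre's step to the IRB. It does not remove it, because nothing says that the shortest deadline governs.

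A reader might infer more than the documents support:

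- **That one event faces every outcome, from 2 working days to no report.** The two deadlines in 11.1 are alternatives. The explicit instruction not to submit covers unrelated or consent-listed events, and only on the off-site form.
- **That serious events at the second site go unseen.** The 24-hour notice rules this out.
- **That the named fatal risks of everolimus are what would be delayed.** Infection, renal failure and pneumonitis, including fatal outcomes, are described in Section 7.3. They would generally count as expected, and the 2-day rule covers unexpected events.
- **That a number of patients can be attached.** Applying an assumed site share to the 33 planned patients would count enrollees, not SAEs in the conflicting categories. The documents give neither a site share nor a rate for such events.

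**Conclusion.** The inconsistency is real and limited to IRB reporting of participating-site SAEs. For an unexpected, possibly related grade 3-4 SAE, the IRB report is due in 2 working days under 11.4.1.3. Under 11.1 (subsites) it is due in 5 working days or at annual review, and it falls outside the 48-hour rule of 11.2. Unrelated grade 3-4 SAEs are due in 5 working days under 11.4.1.3 and 11.2, but can wait for annual review under 11.1.

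This conclusion rests on the current wording and on the absence of any statement of precedence. It does not depend on which form the second site uses; the missing category and the instructions not to submit do. No endpoint, sample size or analysis is affected. The two time limits for unanticipated problems are a minor drafting conflict in the same section.

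**What to change.** Reconcile the passages by amendment:

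1. Set one IRB timetable for both sites, by grade, expectedness and causality. In 11.1 (subsites), replace the amendment or annual-review branch with a cross-reference to it, and align 11.2 (coordinating site).
2. Use one causality threshold throughout, consistent with Section 11.3.1, where possible counts as related.
3. State a deadline for expected, related grade 3-4 SAEs, which 11.4.1.3 now leaves to continuing review. Adopting 11.4.1.3 unchanged would keep that gap.
4. Add a protocol note that this timetable and the Section 11.3.1 scale override the Appendix D form's instructions for this trial's own second site. A note avoids having to revise an institutional form. State which IRB and which form that site uses.
5. Reconcile the 10 working days and the 5 days for unanticipated problems in 11.1 (subsites).

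The choice of deadlines belongs to the sponsor and the IRB; what is needed is that the sections agree. The cost is amendment wording and a few more expedited reports from the second site.
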